8.3. Clinical Laboratory Analyses

Laboratory evaluations including the analyses of chemistry laboratory tests, hematology laboratory tests, urinalysis, and liver function tests will be based on GSK Core Data Standards. Division of Microbiology and Infectious Diseases (DMID) grading for all parameters as specified in the protocol will be assigned programmatically by PPD in the Laboratory Analysis Dataset. The details of the planned displays are in [Appendix 10: List of Data Displays](#).

8.4. Other Safety Analyses

The analyses of non-laboratory safety test results including ECGs and vital signs will be based on GSK Core Data Standards, unless otherwise specified. The details of the planned displays are presented in [Appendix 10: List of Data Displays](#).

10. APPENDICES

10.1. Appendix 1: Schedule of Activities

10.1.1. Protocol Defined Time and Events Table

Table 3 Part 1 Adult Participants

Procedure ¹	Check-in	Treatment Period 1 (Days)				Treatment Period 2 (Days)				Treatment Period 3 (Days)			Follow-up (7 [±3] days after last dose) or Early Termination	Notes
	-1	1	2	3	4	5	6	7	8	9	10	11		
Confined to clinic	X	X	X	X	X	X	X	X	X	X	X	X		
Inclusion and exclusion criteria	X													Recheck clinical status before study intervention
Brief physical examination ²	X											X	X	
Pregnancy test	X												X	Urine pregnancy test (if WOCBP), as appropriate (see Table 10 in Protocol)
Drug, alcohol, and cotinine screen	X													See Table 10 in Protocol

Procedure ¹	Check-in	Treatment Period 1 (Days)				Treatment Period 2 (Days)				Treatment Period 3 (Days)			Follow-up (7 [±3] days after last dose) or Early Termination	Notes
	-1	1	2	3	4	5	6	7	8	9	10	11		
Laboratory assessments	X				X				X			X	X	Including serum chemistry, hematology, and urinalysis (see Appendix 2 in Protocol)
12-lead ECG ³	X	X	X	X		X	X	X		X	X	X	X	See Table 4 , Table 5 , and Table 6 for timing of assessments
ECG Holter monitoring ⁴	X	X	X		X	X	X		X	X	X			See Table 4 , Table 5 , and Table 6 for timing of assessments
Vital signs	X	X	X	X		X	X	X		X	X	X	X	See Table 4 , Table 5 , and Table 6 for timing of assessments
Study intervention		X				X				X				See Table 4 , Table 5 , and Table 6 for time points

Procedure ¹	Check-in	Treatment Period 1 (Days)				Treatment Period 2 (Days)				Treatment Period 3 (Days)			Follow-up (7 [±3] days after last dose) or Early Termination	Notes
	-1	1	2	3	4	5	6	7	8	9	10	11		
Blood collection for pharmacokinetics		X	X	X		X	X	X		X	X	X		See Table 4 , Table 5 , and Table 6 for time points
Urine collection for pharmacokinetics		X	X	X		X	X	X		X	X	X		See Table 4 , Table 5 , and Table 6 for time points
AE/SAE review	X	←-----→											X	
Concomitant medication review	X	←-----→											X	

AE = adverse event, ECG = electrocardiogram, SAE = serious AE; WOCBP = woman of childbearing potential.

- ¹ When coinciding with safety and/or pharmacokinetic assessments, ECGs, vital signs, and pharmacokinetic blood collections should be performed in said order.
- ² A brief physical examination will include, at a minimum, assessments of the skin, lungs, cardiovascular system, and abdomen (liver and spleen).
- ³ Triplicate 12-lead ECGs will be measured on Day -1.
- ⁴ ECG Holter monitoring will begin approximately 12 hours prior to first dose until 24 hours after dosing of each treatment period.

Table 3: Part 2 Adolescent Participants

Procedure ¹	Check-in	Treatment Period 1 (Days)			Check-in ²	Treatment Period 2 (Days)			Follow-up (7 [±3] days after last dose) or Early Termination	Notes
	-1	1	2	3	-1	1	2	3		
Confined to clinic	X	X	X	X	X	X	X	X		Treatment Period 1 and Treatment Period 2 may be separated by 7 days but no more than 10 days.
Inclusion and exclusion criteria	X				X					Recheck clinical status before study intervention
Brief physical examination ³	X				X			X	X	
Pregnancy test	X				X				X	Urine pregnancy test (if WOCBP), as appropriate (see Table 10 in Protocol)
Drug, alcohol, and cotinine screen	X				X					See Table 10 in Protocol
Laboratory assessments	X			X	X			X	X	Including serum chemistry, hematology, and urinalysis (see Appendix 2 in Protocol)
12-lead ECG ⁴	X	X	X	X	X	X	X	X	X	See Table 7, Table 8, and Table 9 for timing of assessments
ECG Holter monitoring ⁵	X	X	X		X	X	X			See Table 7, Table 8, and Table 9 for timing of assessments
Vital signs	X	X	X	X	X	X	X	X	X	See Table 7, Table 8, and Table 9 for timing of assessments
Study intervention		X				X				See Table 7, Table 8, and Table 9 for time points

Procedure ¹	Check-in	Treatment Period 1 (Days)			Check-in ²	Treatment Period 2 (Days)			Follow-up (7 [±3] days after last dose) or Early Termination	Notes
	-1	1	2	3	-1	1	2	3		
Blood collection for pharmacokinetics		X	X	X		X	X	X		See Table 7 , Table 8 , and Table 9 for time points
Urine collection for pharmacokinetics		X	X	X		X	X	X		See Table 7 , Table 8 , and Table 9 for time points
AE/SAE review	X	←=====→							X	
Concomitant medication review	X	←=====→							X	

AE = adverse event, ECG = electrocardiogram, SAE = serious AE; WOCBP = woman of childbearing potential.
 
¹ When coinciding with safety and/or pharmacokinetic assessments, ECGs, vital signs, and pharmacokinetic blood collections should be performed in said order.
 
² Check-in procedures only necessary if participant leaves the clinic between Treatment Period 1 and Treatment Period 2.
 
³ A brief physical examination will include, at a minimum, assessments of the skin, lungs, cardiovascular system, and abdomen (liver and spleen).
 
⁴ Triplicate 12-lead ECGs will be measured on Day -1 (before each treatment period).
 
⁵ ECG Holter monitoring will begin approximately 12 hours prior to first dose until 24 hours after dosing of each treatment period.
										

10.1.2. Protocol Defined Safety and PK Assessments

Table 4 Safety and PK Assessments - Part 1, Period 1

Procedure ¹	Treatment Period 1 Time point (hours)															
	Predose	0	0.5	1	1.5	2	2.5	3	4	6	8	12	24	36	48	
12-lead ECG ²	X		X	X	X	X	X	X	X	X	X	X	X	X	X	
ECG Holter monitoring	X	X														
Vital signs	X				X	X			X		X	X	X	X	X	
Study intervention		X														
Blood PK sample	X		X	X	X	X	X	X	X	X	X	X	X	X	X	
Urine PK collection ³	X	X				X				X	X	X	X	X	X	

ECG = electrocardiogram; PK = pharmacokinetic.

- When coinciding with safety and/or PK assessments, ECGs, vital signs, and PK blood collections should be performed in said order.
- Triplicate 12-lead ECGs will be measured at predose. Single 12-lead ECGs will be measured at all other time points.
- Urine collection intervals include 0 (predose), 0 to 2 hours, 2 to 4 hours, 4 to 6 hours, 6 to 8 hours, 8 to 12 hours, 12 to 24 hours, 24 to 36 hours, and 36 to 48 hours.

Table 5 Safety and PK Assessments - Part 1, Period 2 (12-Hour Dose Interval)

Procedure ¹	Treatment Period 2 Time point (hours)																								
	Predose	0	0.5	1	1.5	2	2.5	3	4	6	8	12	12.5	13	13.5	14	14.5	15	16	18	20	24	36	48	60
12-lead ECG ²	X		X	X	X	X	X	X	X	X	X	X	X	X	X	X	X	X	X	X	X	X	X	X	X
ECG Holter monitoring	X	X																							
Vital signs	X				X	X			X		X	X			X	X				X		X	X	X	X
Study intervention		X										X													
Blood PK sample	X		X	X	X	X	X	X	X	X	X	X	X	X	X	X	X	X	X	X	X	X	X	X	X
Urine PK collection ³	X	X				X				X	X	X	X				X				X	X	X	X	X

ECG = electrocardiogram; PK = pharmacokinetic.

- 1 When coinciding with safety and/or PK assessments, ECGs, vital signs, and PK blood collections should be performed in said order.
- 2 Triplicate 12-lead ECGs will be measured at predose. Single 12-lead ECGs will be measured at all other time points.
- 3 Urine collection intervals include 0 (predose), 0 to 2 hours, 2 to 4 hours, 4 to 6 hours, 6 to 8 hours, 8 to 12 hours, 12 to 14 hours, 14 to 16 hours, 16 to 18 hours, 18 to 20 hours, 20 to 24 hours, 24 to 36 hours, 36 to 48 hours, and 48 to 60 hours.

Table 6 Safety and PK Assessments - Part 1, Period 3 (6-Hour Dose Interval)

Procedure ¹	Treatment Period 3																								
	Predose	Time point (hours)																							
	0	0.5	1	1.5	2	2.5	3	4	6	6.5	7	7.5	8	8.5	9	10	12	14	18	24	36	48	60		
12-lead ECG ²	X		X	X	X	X	X	X	X	X	X	X	X	X	X	X	X	X	X	X	X	X	X	X	
ECG Holter monitoring	X	X																							
Vital signs	X				X	X			X				X	X			X		X	X	X	X	X	X	
Study intervention		X							X																
Blood PK sample	X		X	X	X	X	X	X	X	X	X	X	X	X	X	X	X	X	X	X	X	X	X	X	
Urine PK collection ³	X	X			X			X	X			X			X	X	X	X	X	X	X	X	X		

ECG = electrocardiogram; PK = pharmacokinetic.

- 1 When coinciding with safety and/or PK assessments, ECGs, vital signs, and PK blood collections should be performed in said order.
- 2 Triplicate 12-lead ECGs will be measured at predose. Single 12-lead ECGs will be measured at all other time points.
- 3 Urine collection intervals include 0 (predose), 0 to 2 hours, 2 to 4 hours, 4 to 6 hours, 6 to 8 hours, 8 to 10 hours, 10 to 12 hours, 12 to 14 hours, 14 to 18 hours, 18 to 24 hours, 24 to 36 hours, 36 to 48 hours, and 48 to 60 hours.

Table 7 Safety and PK Assessments - Part 2, Period 1

Procedure ¹	Treatment Period 1 Time point (hours)															
	Predose	0	0.5	1	1.5	2	2.5	3	4	6	8	12	24	36	48	
12-lead ECG ²	X	X	X	X	X	X	X	X	X	X	X	X	X	X	X	
ECG Holter monitoring	X	X														
Vital signs	X				X	X			X		X	X	X	X	X	
Study intervention		X														
Blood PK sample	X		X	X	X	X	X	X	X	X	X	X	X	X	X	
Urine PK collection ³	X	X			X			X	X	X	X	X	X	X	X	

ECG = electrocardiogram; PK = pharmacokinetic.

¹ When coinciding with safety and/or PK assessments, ECGs, vital signs, and PK blood collections should be performed in said order.

² Triplicate 12-lead ECGs will be measured at predose. Single 12-lead ECGs will be measured at all other time points.

³ Urine collection intervals include 0 (predose), 0 to 2 hours, 2 to 4 hours, 4 to 6 hours, 6 to 8 hours, 8 to 12 hours, 12 to 24 hours, 24 to 36 hours, and 36 to 48 hours.

Note: The number of PK samples and the PK sampling time points may be modified based on the adult PK data from Part 1.

Table 8 Safety and PK Assessments - Part 2, Period 2 (if 6-hour dose interval is selected)

Procedure ¹	Treatment Period 2 Time point (hours)																							
	Predose	0	0.5	1	1.5	2	2.5	3	4	6	6.5	7	7.5	8	8.5	9	10	12	14	18	24	36	48	60
12-lead ECG ²	X		X	X	X	X	X	X	X	X	X	X	X	X	X	X	X	X	X	X	X	X	X	X
ECG Holter monitoring	X	X																						
Vital signs	X				X	X			X				X	X			X		X	X	X	X	X	X
Study intervention		X								X														
Blood PK sample	X		X	X	X	X	X	X	X	X	X	X	X	X	X	X	X	X	X	X	X	X	X	X
Urine PK collection ³	X	X			X			X	X			X			X	X	X	X	X	X	X	X	X	

ECG = electrocardiogram; PK = pharmacokinetic.

¹ When coinciding with safety and/or PK assessments, ECGs, vital signs, and PK blood collections should be performed in said order.

² Triplicate 12-lead ECGs will be measured at predose. Single 12-lead ECGs will be measured at all other time points.

³ Urine collection intervals include 0 (predose), 0 to 2 hours, 2 to 4 hours, 4 to 6 hours, 6 to 8 hours, 8 to 10 hours, 10 to 12 hours, 12 to 14 hours, 14 to 18 hours, 18 to 24 hours, 24 to 36 hours, 36 to 48 hours, and 48 to 60 hours.

Note: The number of PK samples and the PK sampling time points may be modified based on the adult PK data from Part 1.

Table 9 Safety and PK Assessments - Part 2, Period 2 (if 12-hour dose interval is selected)

Procedure ¹	Treatment Period 2																										
	Time point (hours)																										
	Predose	0	0.5	1	1.5	2	2.5	3	4	6	8	12	12.5	13	13.5	14	14.5	15	16	18	20	24	36	48	60		
12-lead ECG ²			X	X	X	X	X	X	X	X	X	X	X	X	X	X	X	X	X	X	X	X	X	X	X	X	
ECG Holter monitoring	X									X																	
Vital signs					X	X			X		X	X			X	X					X		X	X	X	X	
Study intervention		X										X															
Blood PK sample	X		X	X	X	X	X	X	X	X	X	X	X	X	X	X	X	X	X	X	X	X	X	X	X	X	
Urine PK collection ³	X		X				X			X	X	X	X				X			X	X	X	X	X	X	X	X

ECG = electrocardiogram; PK = pharmacokinetic.

¹ When coinciding with safety and/or PK assessments, ECGs, vital signs, and PK blood collections should be performed in said order.

² Triplicate 12-lead ECGs will be measured at predose. Single 12-lead ECGs will be measured at all other time points.

³ Urine collection intervals include 0 (predose), 0 to 2 hours, 2 to 4 hours, 4 to 6 hours, 6 to 8 hours, 8 to 12 hours, 12 to 14 hours, 14 to 16 hours, 16 to 18 hours, 18 to 20 hours, 20 to 24 hours, 24 to 36 hours, 36 to 48 hours, and 48 to 60 hours.

Note: The number of PK samples and the PK sampling time points may be modified based on the adult PK data from Part 1.

10.2. Appendix 2: Study Phases and Treatment Emergent Adverse Events

10.2.1. Treatment States

Assessments and events will be classified according to time of occurrence relative to the start and/or stop date of the study treatment for the respective treatment period.

10.2.1.1. Treatment States for Safety Data

Treatment State	Definition
Pre-Treatment	Date/Time < Study Treatment Start Date/Time
On-Treatment	Study Treatment Start Date/Time ≤ Date/Time ≤ Study Treatment Stop Date/Time + 2 Days
Post-Treatment	Date/Time > Study Treatment Stop Date/Time +2 Days

NOTES:

- If the study treatment stop date is missing then the assessment will be considered to be On-Treatment

10.2.1.2. Treatment States for AE Data

Treatment State	Definition
Pre-Treatment	AE Start Date/Time < Study Treatment Start Date/Time
On-Treatment	If AE onset date/time is on or after treatment start date/time & on or before the treatment stop date/time with 2 days lag time Study Treatment Start Date/Time ≤ AE Start Date/Time ≤ Study Treatment Stop Date/Time + 2 Days
Post-Treatment	If AE onset date/time is after the treatment stop date/time with 2 days lag time AE Start Date/Time > Study Treatment Stop Date/Time + 2 days
Onset Time Since First Dose (Days)	If Treatment Start Date/Time > AE Onset Date/Time = AE Onset Date - Treatment Start Date If Treatment Start Date/Time ≤ AE Onset Date/Time = AE Onset Date - Treatment Start Date +1 Missing otherwise
Duration (Days)	AE Resolution Date – AE Onset Date + 1
Drug-related	If relationship is marked 'YES' on eCRF OR value is missing

NOTES:

- If the study treatment stop date is missing then the AE will be considered to be On-Treatment.

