5.3. Lifestyle Considerations

5.3.1. Meals and Dietary Restrictions

- All doses of study intervention (gepotidacin or placebo) should be after food consumption (a standard meal) and with approximately 240 mL of water. Up to 480 mL of water is allowed if the participant has difficulty swallowing multiple tablets.
- Prior to the morning dose, participants will fast (no food or drink except water) for approximately 8 to 10 hours before dosing and will receive a standard meal 30 minutes prior to dose. Participants should consume this meal in 30 minutes or less. Dose administration will occur within 5 minutes of completion of meal consumption. Participants will not receive any further food until 2 hours after dosing. Standard meals will be provided during the study treatment period at times that do not interfere with study procedures.
- For doses scheduled to occur 6 or 12 hours after the initial dose, participants will have the standard meal in the morning and will receive another standard meal (similar in calorie content and similar ratios of protein, carbohydrates, and fat as the previous meal) prior to the second dose. Participants should consume this meal in 30 minutes or less. Dose administration will occur within 5 minutes of completion of meal consumption. Participants will not receive any further food until 2 hours after dosing.
- Refrain from consumption of red wine, Seville oranges, grapefruit or grapefruit juice, pomelos, exotic citrus fruits, grapefruit hybrids, or fruit juices from 7 days before the start of dosing until after collection of the final PK sample.
- No water is allowed until 2 hours after dosing, unless administered under the investigator's direct order for treatment of an AE. Water is allowed ad libitum at all other times.
- Standard meals will be provided during the study dosing period at specified times.

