2.3. Study Design

Dosing
	
Part 1 – Adult Participants:
 
 • Treatment A: Single dose 1500 mg (Period 1) • Treatment B: Matching placebo (Period 1) • Treatment C: Two 3000 mg doses given at Hour 0 and Hour 12 (Period 2) • Treatment D: Two matching placebo doses given at Hour 0 and Hour 12 (Period 2) • Treatment E: Two 3000 mg doses given at Hour 0 and Hour 6 (Period 3) • Treatment F: Two matching placebo doses given at Hour 0 and Hour 6 (Period 3) 
Part 2 - Adolescent Participants
 
 • Treatment A: Single dose 1500 mg (Period 1) • Treatment B: Matching placebo (Period 1) • Treatment G: Two 3000 mg doses (Period 2; exact dosing interval to be determined after Part 1 is complete) • Treatment H: Two matching placebo doses (Period 2; exact dosing interval to be determined after Part 1 is complete)

Time and Events
	
 • See Appendix 1: Schedule of Activities (SoA)

Treatment Assignment
	
 • Part 1 – Adult Participants: Participants will be randomly assigned to receive either all active treatment (gepotidacin, Treatment A/C/E) or placebo (Treatment B/D/F) for all 3 periods • Part 2 – Adolescent Participants: Participants will be randomly assigned to receive either all active treatment (gepotidacin, Treatment A/G) or placebo (Treatment B/H) for both periods.

Interim Analysis
	
The interim analysis will consist data management listings and WinNonLin outputs. Preliminary plasma PK and safety results from participants in Part 1 will be reviewed by the sponsor before enrolling participants into the next part of the study. The dosing interval to be used when two gepotidacin doses are given in Part 2, Period 2 will be determined after a review of the PK and safety results from Part 1. The number of PK samples and the PK sampling time points may be modified based on the adult PK data from Part 1.
 
An ad hoc review of 12-lead electrocardiogram (ECG) data may be performed between Part 1, Period 2 and Part 1, Period 3.

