8.2.1. Acetylcholinesterase-Inhibition AESIs

Any reported AE listed in the table below with a start time no later than 12 hours after the last dose administered in each treatment period, as evaluated by the investigator as per the DMID grading criteria provided in protocol Section 10.8 Appendix 8: Division of Microbiology and Infectious Disease Adult Toxicity Tables for Adverse Event Assessment, will be programmatically identified as Acetylcholinesterase inhibition related AESI.

Table 1 List of AEs for programming to be considered due to Acetylcholinesterase-Inhibition

 • Respiratory 
 ○ Bronchospasm (acute) ○ Dyspnea ○ Bronchorrhea

 • Gastrointestinal 
 ○ Nausea ○ Vomiting ○ Diarrhea ○ GI cramping and pain

 • Cardiovascular 
 ○ Bradycardia

 • Neurological 
 ○ Seizure/Convulsions ○ Vasovagal syncope ○ Salivation ○ Lacrimation ○ Diaphoresis/sweating

AESIs will be listed and tabulated, and a Cumulative Grade will be determined, calculated by the sum of the grade of each reported AE. This enables both the number of AEs and the severity of each AE to be taken into account. For instance, if two AEs in the table above are reported, one of Grade 1 and the other of Grade 3 according to DMID, the total grade of 4 would result in a Cumulative Grade 2 per [Table 2](#) below.

Table 2 Cumulative Grading of Acetylcholinesterase AESI

	Cumulative Grade 1	Cumulative Grade 2	Cumulative Grade 3	Cumulative Grade 4
Total Grade of Signs & Symptoms	1 to 3	4 to 6	7 to 10	≥ 11

The details of the planned displays are provided in [Appendix 10: List of Data Displays](#).

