10.10.6. Safety Figures

Safety Tables					
No.	Population	IDSL / TST ID / Example Shell	Title	Programming Notes	Deliverable [Priority]
Adverse Events					
2.1	Safety	AE10	Gastrointestinal Adverse Events of Special Interest Adverse Events	Part 1, Part 2, and combined	SAC [1]
2.2	Safety	SAFE_F1	Plot of Distribution of Cumulative Grades of Acetylcholinesterase-Inhibition Adverse Events of Special Interest	Combine Part 1 and Part 2 in one page	SAC [1]
2.3	Safety	SAFE_F2	Plot of duration and severity of Adverse Events for Individual Participants	Part1 and Part 2	SAC [1]

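### The SAP derives AE duration and onset in whole calendar days from dates alone, so these variables cannot describe events shorter than a day (minor)

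*SAP*

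**What the plan says.** The table of AE treatment states in SAP 10.2.1.2 gives duration, in days, as "AE Resolution Date – AE Onset Date + 1". For events starting at or after treatment start, onset time is "AE Onset Date - Treatment Start Date +1", also in days and counted from the first dose. Neither formula uses a clock time.

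The same table does use clock time to decide whether an event is on treatment: "Study Treatment Start Date/Time ≤ AE Start Date/Time ≤ Study Treatment Stop Date/Time + 2 Days". SAP 8.2.1 uses it again, selecting cholinergic (acetylcholinesterase-inhibition) AESIs "with a start time no later than 12 hours after the last dose administered in each treatment period". Listings 23 and 24 in SAP 10.10.9 flag AESIs that start within 6 hours of the last dose.

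The named display of duration is Safety Figure 2.3 in SAP 10.10.6, "Plot of duration and severity of Adverse Events for Individual Participants". SAP 10.5.2.1 sets imputation rules for partial AE dates so that time to onset and duration can be calculated.

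On dosing, SAP 2.3 places the second dose at Hour 12 (Part 1, Period 2) or Hour 6 (Part 1, Period 3). Protocol 5.3.1 shows that the first dose is given in the morning ("Prior to the morning dose, participants will fast") but states no hour. Protocol 2.1 calls the cholinergic AEs mild and transient and gives no length in hours.

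**The concern.** The AEs that matter most here are acute. Protocol 2.3.1 relates the cholinergic effects to Cmax, and Protocol 10.7 treats diarrhea during dosing or within 12 hours after it as possibly cholinergic. A variable in whole days cannot resolve such events. Because both doses are given on the same date, day-level onset also cannot tell an event after dose 1 from one after dose 2.

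The error need not be equal across regimens either. After a morning first dose, the Hour 12 dose falls in the evening and the Hour 6 dose in the afternoon. A short event soon after the second dose is therefore more likely to cross midnight, and gain a day, under the 12-hour regimen.

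Safety is a primary objective, and only about 14 adults receive active drug. Figure 2.3 will be read event by event, so a clock-time artefact could look like a difference between regimens.

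**Working it through.** **Inputs from the documents.** The two day-count formulas in SAP 10.2.1.2; the second dose at +12 h or +6 h (SAP 2.3); a morning first dose (Protocol 5.3.1); the AESI onset window, up to 12 h after the last dose (SAP 8.2.1).

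**Assumptions, because the documents give no values.** First dose at 07:00 to 10:00; event length L of 1 to 6 h; onset lag u after dose 2 uniform over a window (a, b). The plan states no figure of its own to reproduce.

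**Limits of the rule (no assumption needed).** One minute across midnight: 1 + 1 = 2 days. Almost 24 h within one date: 0 + 1 = 1 day.

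**Worked events, first dose at 08:00** (dose 2 at 20:00 or 14:00):

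| Onset after dose 2 | Length | 12 h regimen | 6 h regimen |
|---|---|---|---|
| 2 h | 3 h | 22:00-01:00, 2 days | 16:00-19:00, 1 day |
| 2 h | 1 h | 22:00-23:00, 1 day | 16:00-17:00, 1 day |
| 5 h | 2 h | 01:00-03:00, 1 day (onset day 2) | 19:00-21:00, 1 day (onset day 1) |
| 8 h | 3 h | 04:00-07:00, 1 day | 22:00-01:00, 2 days |

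The same short event can score 2 against 1, 1 against 1, or 1 against 2.

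**Share recorded as 2 days.** For a first dose at clock hour h, midnight falls M hours after dose 2, with M = 12 − h (12 h regimen) or 18 − h (6 h regimen). An event crosses midnight when M − L < u < M, so

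share = max{0, min(b, M) − max(a, M − L)} / (b − a).

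Example: 08:00, L = 3, window 0.5 to 4 h. In the 12 h regimen M = 4, so u must lie between 1 and 4, and the share is 3.0/3.5 = 86%. In the 6 h regimen M = 10, so u must exceed 7, which is outside the window, and the share is 0%.

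Early onset, window 0.5 to 4 h; each cell gives the 12 h / 6 h regimen in %:

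| First dose | M (h) | L = 1 h | 2 h | 3 h | 4 h | 6 h |
|---|---|---|---|---|---|---|
| 07:00 | 5 / 11 | 0 / 0 | 29 / 0 | 57 / 0 | 86 / 0 | 100 / 0 |
| 08:00 | 4 / 10 | 29 / 0 | 57 / 0 | 86 / 0 | 100 / 0 | 100 / 0 |
| 09:00 | 3 / 9 | 29 / 0 | 57 / 0 | 71 / 0 | 71 / 0 | 71 / 29 |
| 10:00 | 2 / 8 | 29 / 0 | 43 / 0 | 43 / 0 | 43 / 0 | 43 / 57 |

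Wide window, 0.5 to 12 h, L = 3 h:

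- 07:00 and 08:00: 3/11.5 = 26% in both regimens.
- 09:00: 2.5/11.5 = 22% against 26%.
- 10:00: 1.5/11.5 = 13% against 26%.

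Over 0 to 12 h, 1 h and 2 h events give 1/12 = 8% and 2/12 = 17% in both regimens at all four dose times.

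**After the change.** An event starting 2 h after dose 2 and lasting 3 h is recorded as onset 2 h, duration 3 h in both regimens.

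**The case against.** A reader might infer that the rule systematically makes AEs look longer under the 12-hour regimen. The documents do not support that. They give no dose clock time, onset lag or event length. The 86% against 0% contrast is the most unfavourable dose time for a 3-hour event with early onset, and it disappears or reverses over the full AESI window. Early onset is plausible because the effects track Cmax, but it remains an assumption.

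A reader might also infer that the variable distorts the choice between 6 and 12 hours for Part 2. SAP 3.1 bases that review on data management listings and WinNonlin output. Figure 2.3 belongs to the final deliverable, after all participants have completed. No link is shown.

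Other limits also stand. Cholinergic AESIs are already selected and flagged on hours since the last dose, and SAP 10.3.2 has listings show planned and actual time relative to dosing. The onset weakness is therefore confined to the derived day-count variable. No table in SAP 10.10.5 summarises duration, the cumulative grade in SAP 8.2.1 uses grades only, and the safety analysis is descriptive. The layout of Figure 2.3 is not given, so it might be drawn from start and stop times rather than from the derived variable. No AE stop time is documented.

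None of this changes the stated formula: it counts dates, and it is the only definition of duration in the SAP.

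**Conclusion.** The point holds as a minor one. Without any assumption, the derived duration cannot describe events shorter than a day, and the derived onset cannot separate two doses given on one date.

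An unequal error between regimens is possible but conditional. With early onset and a 07:00 to 10:00 first dose, events of 1 to 4 hours are counted as 2 days in 0% to 100% of cases after the Hour 12 dose and in none after the Hour 6 dose. Six-hour events with a 10:00 dose reverse the order (43% against 57%). With onset spread over 12 hours, the difference for 3-hour events is nil or goes the other way.

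What is affected is final descriptive reporting: Figure 2.3, if it uses this variable, and any listing that shows it. An effect on the Part 2 interval decision is not shown.

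**What to change.** In SAP 10.2.1.2:

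- Derive duration in hours as AE stop date/time minus AE start date/time.
- Derive onset in hours from the most recent dose, and add a flag for dose 1 or dose 2.
- Use these variables in Figure 2.3 and the AE listings, for both study parts.
- Keep the calendar-day form only where a clock time is missing, and mark those records.

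The cost is a wording change and a few lines of programming. Dose times are already recorded (Protocol 6.4) and AE start times are already used. The one thing to confirm is that the eCRF collects the AE stop time; if it does not, one time field has to be added, and events already recorded without it stay on the marked calendar-day form.
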